7.3. Duration of study

For each patient initiating treatment, a minimum follow-up period of 2 years will be observed.

8. SOURCE OF INFORMATION AND DATA MANAGEMENT.

8.1. Source of information

The information for this study will be obtained from the patient's medical records and the interview that the physician and dietitians/nutritionists carry out with the patient. All information will be recorded on the forms designed for this purpose (Annex 3) and subsequently submitted to the coordinating center, prior express authorization of the patient by signing the Informed Consent, for its statistical analysis.

The corresponding data will be saved in a file owned by PronoKal Group®, who will manage the information according to Organic Law 15/1999 relative to Protection of Personal Data.

9. ENDPOINTS

9.1. Primary endpoints

The primary variables to be recorded for the study objectives are:

- Consumption of health resources: visits, laboratory controls, admissions ...
- Changes in pharmacological treatment
- Work absenteeism

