5.1. Inclusion criteria

- Patients of both sexes 18 years of age or older
- Patients with overweight or obesity ($BMI > 30 \text{ kg/m}^2$) with at least one or more of the following comorbidities associated with obesity:

- Type 2 diabetes mellitus
- Arterial hypertension
- Dyslipidemia
- Hyperuricemia

Those who are under pharmacological treatment with two or more drugs (oral antidiabetic and/or lipid-lowering agents and/or antihypertensive and/or hypouricemic agents)

- Patients who agree to attend the follow-up visits at the Pronokal centre, in Buenos Aires.
- Patients who agree to participate and provide a signed informed consent

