5.3. Number of patients

Expected number of subjects is 200 patients. Subjects who initiate the multidisciplinary weight loss treatment during the study inclusion period, meet the inclusion and exclusion criteria, and agree to participate and sign the informed consent will be included in the study.

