10.2. Analysis of objectives

The primary objective analysis will include:

- Costs of weight loss treatment estimated from the cost of: protein products and dietary supplements + number of control visits + number of laboratory tests performed
- Healthcare expenditure estimated as the sum of the following costs: pharmacological treatment of associated comorbidities, incidence of

complications (visits to his/her primary care physician, a specialist or emergency department for acute complications, treatment of acute complications, number of hospital admission days, antibiotic treatment), consumption of health resources (visits to the general practitioner, visits to specialists, laboratory tests)

- Work absenteeism, estimate of the number of work leave days + hours of work absenteeism due to health problems or medical visits.

In order to evaluate if the weight loss treatment is improving the health of patients and reducing health expenditure and absenteeism, the healthcare expenses and work absenteeism estimated from the doctor's records corresponding to the 6 months prior to the initiation of the weight loss treatment will be compared with data recorded at follow-up visits over the 2-year follow-up. Likewise, the doses and number of drugs required by patients for the treatment of their comorbidities before the weight loss and at the control visits during weight loss and up to completing the 2 years of follow-up will be compared.

As secondary objectives, the efficacy of the weight loss treatment will be studied by comparing the anthropometric parameters of the initial visit with those of the follow-up visits (weight, body mass index and waist circumference). Likewise, any improvement in laboratory parameters and blood pressure during the follow-up will be studied. Changes in quality of life scores (SF-12) will also be assessed between the initial visit and the end of each treatment stage.

For all objectives, the comparisons between qualitative variables will be made using the Chi square test or the Fisher exact test, and the comparison between quantitative variables will be performed using the Student's t-test (in the case of 2 groups) or by the one-way ANOVA test (for 3 or more groups). If the conditions for the Student's t-test or the Anova test are not met, the non-parametric Mann-Whitney U test (2 groups) or the Kruskal-Wallis test (for 3 or more groups) will be used.

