Safety and tolerability will be analysed by descriptive statistics of all side effects or adverse reactions reported by patients throughout the study.

For all tests, the significance level will be set at $p < 0.05$.

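### Work absenteeism is a primary endpoint with no defined at-risk population: if patients without paid work enter as zeros, the mean change is scaled by the employed share and the unpaired rank fallback loses power

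*Combined protocol and SAP*

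**What the plan says.** All references are to the combined protocol and SAP.

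- Section 9.1 gives three primary variables, one of which is "Work absenteeism". No population is attached to it.
- Section 10.2 defines it as an "estimate of the number of work leave days + hours of work absenteeism due to health problems or medical visits". There is no denominator and no rule for a patient who has no job.
- Section 10.2 compares "the healthcare expenses and work absenteeism estimated from the doctor's records corresponding to the 6 months prior to the initiation of the weight loss treatment" with what is recorded at visits over the 2-year follow-up, in the same patients.
- Section 5.1 admits "Patients of both sexes 18 years of age or older". Nothing in sections 5.1 or 5.2 concerns employment.
- Section 5.3 states "Expected number of subjects is 200 patients", with no calculation behind it.
- For quantitative variables, section 10.2 names Student's t-test for two groups, with no mention of a paired form. If its conditions fail, "the non-parametric Mann-Whitney U test (2 groups) or the Kruskal-Wallis test (for 3 or more groups) will be used".
- Section 7.2 has sociodemographic data recorded at the pre-inclusion visit (day -15), and days and cause of absence recorded by the dietitians at follow-up. Job status is not named in either place.

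**The concern.** The eligible patients are adults of any age with obesity-related comorbidity, so some may be retired, unemployed or working unpaid at home. While a patient has no paid job, absence from work cannot occur, whatever happens to that patient's health. A zero from such a patient does not mean the same as a zero from a worker who missed no days.

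The plan does not separate the two. Three things are at stake on a primary endpoint:

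- If non-workers are scored zero, the reported mean change mixes the effect on workers with the employment mix of the clinic.
- The extra tied zeros weaken the named rank test.
- If non-workers are instead left out, that choice is made without a rule and possibly after the data have been seen.

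**Working it through.** **No figure to reproduce.** The plan states no power, effect size, standard deviation, absence rate or employed share. From the documents come n = 200, the 0.05 level (two-sided assumed, as the sidedness is not stated) and the tests. Everything else below is an assumption.

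**1. Dilution of the mean (exact).** Let *p* be the share in work and *d* the workers' mean reduction. With non-workers at 0 before and after, the whole-cohort mean reduction is *p* × *d* + (1 − *p*) × 0 = *p* × *d*. Take *d* = 4 − 2.4 = 1.6 days, with both periods on a common time scale:

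- 90% in work: 0.90 × 1.6 = 1.44 days
- 75%: 0.75 × 1.6 = 1.20 days
- 60%: 0.60 × 1.6 = 0.96 days

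**2. Mann-Whitney power, first scenario (simulation).** Workers' counts are negative binomial (dispersion 0.5) with a shared gamma(1,1) patient effect and means 4 and 2.4. Non-workers are 0/0. There were 3000 simulated trials per share.

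| Share in work | All 200 | Workers only |
|---|---|---|
| 100% | 0.55 | 0.55 |
| 90% | 0.44 | 0.50 |
| 75% | 0.30 | 0.43 |
| 60% | 0.17 | 0.33 |
| 50% | 0.11 | 0.28 |

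A repeat run gave 0.27 against 0.41 at 75% and 0.16 against 0.35 at 60%. Taking both runs, the loss is about 5 to 6 points at 90%, 13 to 14 at 75% and 16 to 19 at 60%.

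**3. Sensitivity to the absence pattern.** A second simulation (1000 replicates, Monte Carlo SE at most 1.6 points) used six other assumed scenarios. Any absence among workers falls from 40% to 28%, 60% to 45% or 90% to 80%. Days are lognormal with median 4 and log-SD 1, the median ratio is 0.75 to 1.0, and the within-patient correlation is 0 to 0.4.

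| Without a job | Power, workers only | Power, all 200 | Loss (points) |
|---|---|---|---|
| 20% | 68–97% | 64–88% | 4–11 |
| 30% | 61–94% | 55–74% | 6–24 |
| 40% | 50–90% | 42–61% | 7–47 |
| 50% | 47–82% | 17–45% | 11–65 |

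The loss is smallest when absence among workers is rare (4 to 11 points in the 40% to 28% case) and largest when it is common. In the latter case the added zeros make up most of the ties.

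**4. Paired tests.** A zero difference adds nothing to the sum of differences or the sum of squares. If *s* is the SD of the workers' differences, the paired t statistic in all patients is the workers' statistic multiplied by about 1 / √(1 + (1 − *p*)(*d*/*s*)²). For a borderline result (t = 1.96) with 200 × 0.75 = 150 workers, *d*/*s* = 1.96/√150 = 0.160, and the factor is 1/√(1 + 0.25 × 0.0256) = 0.997. The simulations agree: power of the paired t-test was the same with or without non-workers to within a fraction of a point in the second set. The signed-rank test lost nothing, because it drops zero differences. The unpaired t-test lost about 2 to 13 points.

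**5. Would selection on pre-treatment work alone be enough?** No. Patients who start work later are excluded, while those who leave work stay in and move to zero. With a mean of 4 days, no true effect and 10% leaving for the whole follow-up, the apparent benefit is 0.10 × 4 = 0.4 days per worker. In simulation the Mann-Whitney test then rejected in 11–12% of trials, against a nominal 5%.

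**The case against.** **The zeros are inferred.** The plan does not say that patients without a job are scored zero; they could be left blank or marked not applicable. This stands. What is documented is the absence of a rule, and steps 1 to 3 follow only if zeros are entered.

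**The power loss comes from the unpaired test.** This also stands. The comparison is within patients, and a signed-rank test on all 200 would lose nothing. Mann-Whitney is moreover only the fallback, although skewed absence data with many zeros make its use likely. Pairing does not, however, remove the dilution of the mean.

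**The all-patient mean is the right quantity for cost per treated patient.** Given the cost-effectiveness objective in section 3.1, this is correct. It answers a different question from whether absence fell among those who work, and both can be reported.

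**Stronger readings that the documents do not support:**

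- A reader might infer that a patient with no job at entry must score zero in both periods. That patient may have worked earlier in the preceding 6 months or may start work during the 2 years. In the second case the count can rise without any decline in health.
- A reader might infer that job status is not collected. It may sit within the sociodemographic data or on the recording form in Annex 3, which is not in the text available here.
- A reader might infer that the rank test necessarily loses most of its power. The range in step 3 shows that this depends on two figures the documents do not give.

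**Conclusion.** The concern holds in a limited form. A primary endpoint has no stated at-risk population and no scoring rule for patients without paid work. If they are entered as zeros, the mean change shrinks in exact proportion to the employed share. The Mann-Whitney fallback loses roughly 5 points of power at 90% in work and 14 to 19 points at 75% to 60% in the first scenario. Across the second set the loss was 4 to 47 points with 20% to 40% not in work. These power figures rest on assumed absence rates, effect sizes and employed shares; the dilution rests only on zero scoring. Paired tests are essentially unaffected in power, and the whole-cohort mean remains valid as a per-treated-patient input to the cost calculation.

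**What to change.** 1. In section 7.2, name employment status as an item within the sociodemographic data at day -15, covering the preceding 6 months, and again at follow-up visits, with dates of starting or leaving work.
2. In sections 9.1 and 10.2, define the absenteeism analysis in patients with paid work during the 6-month pre-treatment period. Express absence per unit of time in paid work in each period, so that leaving work is not counted as improvement.
3. Compare the two periods with a paired analysis.
4. Report the number of patients contributing, and the number with no paid time in follow-up, for whom no follow-up rate exists.
5. Keep the all-patient mean, with non-workers at zero, for the cost-effectiveness calculation, and label it as such.

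The cost is an n below 200 for this endpoint, one additional form item that may already be in Annex 3, and a few sentences in sections 7.2, 9.1 and 10.2. Patients who start work only after treatment begins fall outside this analysis; their number should be given.

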9.2. Secondary endpoints

- Body weight and waist circumference
- Changes in clinical parameters: glycaemic profile, lipid profile, blood pressure
- Score in the SF-12 quality of life questionnaire
- Onset of side effects
- Onset of serious adverse reactions during the protein diet's follow-up.

10. STATISTIC ANALYSIS

10.1. Descriptive statistics

Descriptive statistics will be made of all the variables collected in the Case Report Form, building frequency tables for the nominal-type variables and measurements of central tendency and dispersion for continuous variables. The 95% confidence intervals (95% CI) will be estimated for the latter.

10.2. Analysis of objectives

The primary objective analysis will include:

- Costs of weight loss treatment estimated from the cost of: protein products and dietary supplements + number of control visits + number of laboratory tests performed
- Healthcare expenditure estimated as the sum of the following costs: pharmacological treatment of associated comorbidities, incidence of

complications (visits to his/her primary care physician, a specialist or emergency department for acute complications, treatment of acute complications, number of hospital admission days, antibiotic treatment), consumption of health resources (visits to the general practitioner, visits to specialists, laboratory tests)

- Work absenteeism, estimate of the number of work leave days + hours of work absenteeism due to health problems or medical visits.

In order to evaluate if the weight loss treatment is improving the health of patients and reducing health expenditure and absenteeism, the healthcare expenses and work absenteeism estimated from the doctor's records corresponding to the 6 months prior to the initiation of the weight loss treatment will be compared with data recorded at follow-up visits over the 2-year follow-up. Likewise, the doses and number of drugs required by patients for the treatment of their comorbidities before the weight loss and at the control visits during weight loss and up to completing the 2 years of follow-up will be compared.

As secondary objectives, the efficacy of the weight loss treatment will be studied by comparing the anthropometric parameters of the initial visit with those of the follow-up visits (weight, body mass index and waist circumference). Likewise, any improvement in laboratory parameters and blood pressure during the follow-up will be studied. Changes in quality of life scores (SF-12) will also be assessed between the initial visit and the end of each treatment stage.

For all objectives, the comparisons between qualitative variables will be made using the Chi square test or the Fisher exact test, and the comparison between quantitative variables will be performed using the Student's t-test (in the case of 2 groups) or by the one-way ANOVA test (for 3 or more groups). If the conditions for the Student's t-test or the Anova test are not met, the non-parametric Mann-Whitney U test (2 groups) or the Kruskal-Wallis test (for 3 or more groups) will be used.

Safety and tolerability will be analysed by descriptive statistics of all side effects or adverse reactions reported by patients throughout the study.

For all tests, the significance level will be set at $p < 0.05$.

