The standardized multidisciplinary method under study (PronoKal® Method) is a personalized weight loss program under medical supervision. Its purpose is to maintain the body's weight through food re-training and the continued support of a team of dietician-nutritionists.

Based on a protein diet, this method is developed according to the characteristics of the patient and contemplates the participation of a multidisciplinary team that includes medical control, dietary-nutritional monitoring, physical activity and emotional support. Thus, the aim is, on the one hand, to produce rapid weight loss, especially at the expense of fat mass, and on the other hand to achieve a long-term maintenance of the results obtained.

Thus, in addition to a dietary pattern, the method contemplates other factors involved in the pathophysiology of obesity, such as nutritional education, physical activity and emotional support, all of which must be combined under medical supervision to ensure a safe clinical progression of the patient.

In addition to weight loss, other aspects need to be modified in the treatment of the obese patient, so that appropriate behaviours are adopted, resulting in the maintenance of the correct weight.

The basic pillars for the treatment of obesity are changes in lifestyle, including a dietary plan, adjustment of physical activity and emotional support. Thus, the management of obesity requires a multidisciplinary approach that adapts to the characteristics of the patient and allows greater effectiveness in the long term and the optimization of healthcare resources used in the fight against obesity.

Under these premises, the clinical application of the method under study is established through the intervention of a Multidisciplinary Specialist Team:

- 1. Doctor:** clinical assessment, treatment prescription and patient follow-up.
- 2. Physical activity:** guidance and advice to perform adequate physical activity, aimed at increasing caloric expenditure and re-adjusting the energy balance.
- 3. Dietitians:** accompany and advise on nutrition and food choices throughout the treatment.
- 4. Psychological support:** reinforcement of the patient's psychological status contributing to boost the patient's motivation in order to reach his/her short, medium and long-term goals.

The aim of this standardized multidisciplinary method is to decrease the weight of obese patients, which is expected to improve the comorbidities associated with obesity

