3. STUDY OBJECTIVES

3.1. Primary objective

To assess the Cost-effectiveness of a standardized weight loss method (PronoKal® Method) treatment to improve the health condition of obese patients with comorbidities and thereby reduce healthcare expenditure (pharmacological treatment, incidence of complications, use of health resources) and work absenteeism.

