6. TREATMENT DESCRIPTION

The standardized multidisciplinary method under study is a weight loss program consisting of different stages. The initial stage (stage 1) is based on a protein diet, a type of ketogenic diet very low in calories. This stage is followed by a physiological adaptation stage (stage 2) in which all food groups are reintroduced progressively, and a maintenance phase (stage 3) with long-term monitoring of the patient's weight to ensure stability of the results obtained. This program contemplates other essential aspects in the management of obese patients, such as dietary education, physical activity and psychological support throughout the treatment.

80% of target weight loss			20% of target weight loss	Long-term maintenance of weight loss
Multidisciplinary team (dietary counselling / physical activity / psychological support)				
Stage 1 Active Stage		Stage 2 Dietary re-education		Stage 3 Maintenance
Phase 1	Phase 2	Phase 3	Gradual re-introduction of different foods	
VLCK diet ¹ (600-800 kcal/day)		LC diet ² (800-1500 kcal/day)		Maintenance diet (1500-2250 kcal/day)

The stage 1 protein diet is established through the intake of high biological value proteins and low-glycaemic vegetables, supplemented with micronutrients (potassium, sodium, calcium, magnesium, vitamins and trace elements) to avoid deficiencies. This stage consists of 3 phases (Phase 1, Phase 2a and Phase 2b), in which a protein preparation and then a second protein preparation are replaced progressively by protein-rich natural foods (meat/fish/eggs). During this period of ketogenic diet, the patient will be visited by the doctor every fortnight.

The ketogenic stage 1 of the method will be maintained for 2 months for those patients with an initial BMI of 30 to 35 kg/m² and for 3 months for those patients with initial BMI > 35 kg/m².

Stage 2 begins after the initial loss of most of the weight to be lost (ideally 80%), with the progressive introduction of different foods, while reducing protein preparations at the same time. In this way the weight loss indicated by the doctor is finally reached and the food balance is also achieved. This stage will be maintained for a period of 4 months in patients with an initial BMI of 30 to 35 kg/m² and for 6 months for those patients with initial BMI > 35 kg/m².

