The last stage of the method begins at this moment, which involves the long-term maintenance of the lost weight, with the supervision and monitoring of specialized dietitians/nutritionists who advise patients in terms of consolidation of their new dietary habits, that is, the establishment of a balanced diet, which is the ultimate goal of the method.

The method must be implemented under strict medical supervision to ensure the efficacy and, above all, the safety of the program. In addition, the program is supported

by dietitians/nutritionists who help control the patient's progress (with continuous on-site and/or telephone follow-up over the 2 years of treatment) and a team of psychological counselling professionals and experts in physical activity.

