7.2. Follow-up period

The expected follow-up period for each patient will be 2 years from the time of inclusion, recording data during the weight loss and maintenance periods. The registry of patient data for this study will be made by the doctor and the dietitians/nutritionists who will regularly see the patient in the face-to-face visits at the Pronokal centre. For this, a specific form will be designed in which information about the variables to be studied will be collected.

Before starting treatment with the standardized multidisciplinary method and its inclusion in the study, the physician will have performed a first patient pre-inclusion visit (day -15) to request complementary tests (laboratory and ECG) and rule out the existence of contraindications to the ketogenic diet part of the weight loss program.

The study will begin with the baseline visit (day 0) in which the inclusion and exclusion criteria will be confirmed, the signing of informed consent will be obtained and the multidisciplinary treatment will be prescribed, followed by 6 control visits: 2 visits during the ketogenic stage (1-month after the start and at the end of ketosis), 2 visits during the physiological adaptation phase (at 4 or 5 months and at the end of stage 2) and 2 follow-up visits during the maintenance up to the 2-year completion. Regardless of the visits established in this protocol, the doctor will make as many visits as he/she deems necessary for good patient control.

On the other hand, dietitians/nutritionists, according to the methodology of the program, will carry out a face-to-face follow-up of the patient, which will be fortnightly during the ketogenic diet, monthly during the physiological adaptation of stage 2 and quarterly or semi-annual during the maintenance stage.

In the **pre-inclusion visit (day -15)**, the physician will perform a first clinical assessment of the patient. He/she will record the sociodemographic data, history of diabetes, comorbidities, pharmacological treatments. He/she will request complete laboratory tests and will perform an electrocardiogram to rule out contraindications and verify the inclusion/exclusion criteria. The said laboratory tests will include:

- Complete blood count and leukocyte formula
- Hydrocarbon metabolism: fasting glycemia, HbA1c, insulinemia
- Lipid profile: total cholesterol, LDL-C, HDL-C, triglycerides
- Transaminases: GOT, GPT, gammaGT

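### The treatment-cost formula in section 10.2 has no term for telephone follow-up and covers other programme support only conditionally, so programme cost may be understated

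*Combined protocol and SAP*

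**What the plan says.** The primary objective in section 3.1 is "To assess the Cost-effectiveness of a standardized weight loss method", that is, of the method as a whole. Section 10.2 lists the cost of weight loss treatment first among the components of that analysis and builds it from three items: "protein products and dietary supplements + number of control visits + number of laboratory tests performed".

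The method itself is described more widely. Section 2 says that it "contemplates the participation of a multidisciplinary team that includes medical control, dietary-nutritional monitoring, physical activity and emotional support". Section 6 refers to "other essential aspects in the management of obese patients, such as dietary education, physical activity and psychological support throughout the treatment". It adds that the dietitians "help control the patient's progress (with continuous on-site and/or telephone follow-up over the 2 years of treatment", and that the programme is also supported by "a team of psychological counselling professionals and experts in physical activity".

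On visits, section 6 states: "During this period of ketogenic diet, the patient will be visited by the doctor every fortnight". Section 7.2 describes a baseline visit "followed by 6 control visits", leaves further doctor visits to the doctor's judgement, and then sets out a separate face-to-face schedule for the dietitians.

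**The concern.** A cost-effectiveness assessment needs the cost of everything the programme delivers. The formula in 10.2 reads as a closed list, and several inputs that sections 2 and 6 present as part of the method are not named in it. The healthcare-expenditure item in 10.2 does not pick them up either: it names general practitioner, specialist and emergency visits, drugs, admissions and laboratory tests.

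Leaving out inputs can lower the programme cost but cannot raise it, so any error favours the method. In addition, 'control visits' is undefined. Two analysts could cost the same patient differently, one counting doctor visits only and the other counting dietitian visits as well.

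**Working it through.** The plan states no cost figure to reproduce. The check has three parts.

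**1. Programme inputs against the formula**

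| Programme input | Where described | Term in the 10.2 formula? |
|---|---|---|
| Protein products, supplements | Section 6 | Yes |
| Laboratory tests | Section 7.2 | Yes |
| Doctor visits | Sections 6, 7.2 | Yes, as control visits (whether the fortnightly and extra visits count is not stated) |
| Dietitian, face to face | Sections 6, 7.2 | Only if 'control visits' includes them |
| Dietitian, telephone | Section 6 | No |
| Psychological support | Sections 2, 6 | Only if given within a control visit |
| Physical-activity support | Sections 2, 6 | Only if given within a control visit |

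**2. What 'control visits' could mean**

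- For doctor visits only: section 7.2 applies the term to the six study visits and introduces the dietitians' follow-up afterwards, as a separate matter.
- For doctor and dietitian visits: section 6 gives the dietitians a role in controlling progress, and section 7.2 speaks of doctor and dietitians together when it describes face-to-face visits at the centre.
- The second use of the term in 10.2, for comparing drug doses, does not settle it, because under section 7.2 both doctor and dietitians record medication changes.

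**3. Scheduled face-to-face dietitian contacts**

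Inputs from sections 6 and 7.2: stage 1 lasts 2 months (BMI 30 to 35) or 3 months (BMI over 35); stage 2 lasts 4 or 6 months; follow-up is 24 months. Dietitian contacts are every two weeks in stage 1, monthly in stage 2, and every 3 or 6 months in maintenance. I take fortnightly as 2 per month and round part-intervals down.

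Contacts = 2 × (stage 1 months) + (stage 2 months) + (maintenance months ÷ 6 or ÷ 3)

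- BMI 30 to 35: maintenance = 24 − 2 − 4 = 18 months. Contacts = 4 + 4 + (18/6 = 3 to 18/3 = 6) = 11 to 14.
- BMI over 35: maintenance = 24 − 3 − 6 = 15 months. Contacts = 6 + 6 + (15/6 = 2.5, counted as 2, to 15/3 = 5) = 14 to 17.

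Across both groups this gives 11 to 17 per patient. On the doctor-only reading none of these has a cost term; on the broad reading all do. Telephone, psychological and activity contacts have no stated frequency and cannot be counted. Without unit costs, none of this converts to money.

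**The case against.** The strongest reply is that the method is presented as one standardized programme, so the price of the products may already pay for the support team. If so, nothing is omitted. This stands as a possibility. The plan gives no price list, costing perspective or source of unit costs, so it can be neither confirmed nor excluded.

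A second reply is that the harm is limited. This also stands. Section 10.2 defines no ratio or net cost that uses treatment cost, and its written before/after comparisons do not use it. A reader might infer that the primary comparisons are biased; the documents do not support that.

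Other strong readings also go too far:

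- *Psychological and activity support can never be costed under the formula.* Section 2 describes the activity component as guidance and advice and the psychological component as reinforcement, and no separate visits are scheduled for either. Such support could be given during a control visit. Section 6 does name separate professionals, so contacts outside such visits are plausible. Only telephone contact falls outside any sense of 'visit'.
- *The contacts will not be recorded.* The recording lists in section 7.2 show no count of telephone, psychological or activity contacts, but they show no count of doctor visits either, and 10.2 clearly means to count visits. The form in Annex 3 was not available to me. Section 9.1 also names visits in an open-ended list without limiting them to doctors.
- *Six control visits against 11 to 17 dietitian visits means that 65% (11/17) to 74% (17/23) of contacts go uncosted.* This leaves out the fortnightly doctor visits in stage 1 and any extra ones, assumes the narrow reading, and counts contacts rather than cost.

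**Conclusion.** The concern holds in a limited form. As written, the formula leaves telephone follow-up without a cost term. It also leaves out any psychological or activity support given outside a control visit, and it costs the 11 to 17 scheduled face-to-face dietitian contacts only on a broad reading of an undefined term.

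If the price does not already include this support, the programme cost as reported would be too low, and so would the cost side of any statement that sets it against savings. The size cannot be derived. The dietitian count shows how much depends on the definition of one term, and it rests on the scheduled frequencies being followed. A reader might conclude that cost is in fact understated; the documents show only that it can be, because the bundling question is open.

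This is a cheap improvement to a component of the primary analysis. It does not invalidate the planned comparisons.

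**What to change.** In section 10.2, replace the count of control visits with all programme contacts actually made, by type: doctor, dietitian face to face, telephone, psychological and physical activity. Give each type a unit cost. Check that the study form counts each type, and add any that are missing. Where the product or programme price already covers a type of support, say so and do not cost it again. If the price covers all of it, one sentence saying so closes the point.

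The cost of the change is one reworded formula, a unit cost per contact type and a little more recording; the form may already hold some of the counts. The programme cost may come out higher.
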